9.6.3 Preparation of DCs or PBMCs for Vaccination

For each vaccination, DCs or PBMCs will be rapidly thawed at 37°C, washed with PBS and counted. The cell concentration will be adjusted to 2×10^7 cells per 400 μ L of preservative free saline containing 150 μ g of GM-CSF for DC vaccines and saline only for PBMC vaccines and loaded into a 1 mL tuberculin syringe with an appropriately sized needle in accordance with **SOP-UFBTIP-1124**.

9.7 Tetanus and Diphtheria Toxoid Booster and site pre-treatment

At time of first vaccination, all patients, regardless of tetanus vaccination history, will receive a Td booster (5 Lf) intramuscularly into the deltoid muscle.

Subjects will undergo vaccine site pretreatment with a one-fifth dose of Td (1 Lf) (treatment arms 1 and 2) or saline (arm 3) intradermally 6-24 hours prior to Vaccine #3, #6, and #9, alternating site for each pretreatment

9.8 DC or PBMC Vaccination

On day 22-24 of the first TMZ cycle, all patient groups will receive their first intradermal immunization in accordance with **SOP-UFBTIP-128** (per randomization assignment). The 2 subsequent immunizations will be given every 2 (+/- 1) weeks for a total of three doses. Each immunization will be divided equally between both inguinal regions with a total volume of 200 μ L per side. Vaccines target dose is 2×10^7 cells. If less cells (DCs or PBMCs) are available at time of vaccination, injection may proceed with available cells and patients will be informed of the lower dose. Patients will be monitored for thirty minutes to one hour post-immunization for the development of any adverse effects. The immunization procedures will be supervised by a nurse or physician that has completed an Advanced Cardiac Life Support (ACLS) course. A cardiac resuscitation cart will be available in the immediate vicinity when performing these immunizations in case of severe allergic reactions.

After vaccine #3, patients will undergo a repeat leukapheresis for PBMCs and immunologic monitoring.

Subsequently, patients will be immunized on day 22-24 of every cycle of TMZ.

Monthly vaccinations will continue until a total of 10 vaccines have been administered or until tumor progression (whichever comes first). Missed vaccines during cycles 1-8 may be given with subsequent cycles of Temozolomide (or monthly for patients off Temozolomide) if there is no tumor progression until patients receive a total of 10 vaccines.

Patients who experienced toxicity during temozolomide adjuvant cycles for whom it is deemed not safe to resume chemo cycles may continue to receive monthly study vaccines at the discretion of the PI in consultation with the treating physician, if the PI believes that it is safe to continue therapy and that patients may benefit from the study treatment. Vaccination with investigational product may be given until the patient receives a total of 10 vaccines or until progression, whichever comes first.

Patients who can no longer receive Temozolomide and start other anti -cancer therapies before experiencing disease progression will not receive additional study vaccines.

Patients who have been enrolled in the study but are no longer eligible to receive study treatment for reasons other than progression are allowed to receive vaccines that have been generated for them at the discretion of the PI. They will be replaced for purposes of study endpoint if they do not meet criteria of an evaluable subject (received standard XRT/TMZ and received at least one DC vaccine). Such subjects would include: subjects who do not complete standard radiation treatment with concomitant TMZ, have prolonged interruption of treatment beyond allowable study guidelines. These patients will be included in the intent to treat analysis but excluded from the evaluable subjects analysis if disqualified prior to receiving first vaccine. Such subjects may receive QA/QC qualified DC vaccines according to study schedule with or without TMZ at discretion of the PI and in consultation with the treating neuro-oncologist (i.e. subjects removed for intolerance of TMZ treatment may discontinue or reduce TMZ dose as clinical management would dictate).

Given absence of curative treatment for GBM, release of vaccines to patients who have consented to the study but are unable to meet study requirements (most often chemotherapy intolerance) is deemed in best interest of the enrolled subjects and best utilization of cGMP manufactured autologous products. While these patients may be excluded from primary endpoint analysis of evaluable subjects, all toxicity monitoring and DLT stopping rules will apply to any subjects receiving DC vaccination.

9.9 MRI/MRS Imaging of DC Migration

All patients will undergo vaccine site pre-treatment with Td (1Lf) ([Martin-Fontech, Sebastiani et al. 2003](#)) or saline 6-24 hours prior to Vaccine #3, #6, and #9.

At vaccine #3, patients at the University of Florida site will undergo MRI/MRS imaging before vaccine site pretreatment, 48hrs post vaccination, and 5 to 7 days post vaccination (optional) to evaluate impact of DC vaccination and unpulsed PBMC vaccination at inguinal draining lymph nodes. MRI/MRS imaging 5 to 7 days post vaccination may be performed when feasible for patients. Regions of interest will be analyzed in a blinded fashion by qualified radiologists within the Advanced Magnetic Resonance Imaging and Spectroscopy (AMRIS) facility and UF Health Department of Radiology. Peripheral blood and urine will be collected at these time points for soluble biomarker analysis. These correlative studies are designed to determine whether changes in VDLNs can be assessed by MRI/MRS and correlation between changes and clinical outcome.

10 STUDY REQUIREMENTS

10.1 Enrollment

- Signed informed consent.
- History, physical & neurological exam
- MMSE for subject \geq 50 years.
- Histopathology report confirming GBM (WHO Grade IV Glioma) and molecular diagnostics.
If molecular testing were not performed at time of diagnosis, promoter hypermethylation of the *O6*-methylguanine-methyl-transferase (*MGMT*) gene, and the mutation status of the *IDH1* and *IDH2* genes will be obtained for study data analysis.
- Preoperative MRI (or CT).
- Postoperative MRI (or CT) within 28 days of study enrollment. If the postoperative MRI is older than 28 days, a new MRI will be obtained prior to patient randomization. The new MRI will serve as baseline MRI.
- Karnofsky Performance Status.
- CBC with differential and CD4+/CD8+ T cell ratio.
- Infectious disease testing to include: HIV, Hepatitis B, Hepatitis C and CMV.
- For females of child-bearing potential, β -HCG serum pregnancy test.
- Pathology slides (if available) consisting of 1 hematoxylin and eosin (H&E) and 19 unstained slides, from all prior resections, prepared on Fischer Plus glass or Histostix coated slides.

- Confirm eligibility.

10.2 Prior to Leukapheresis (Vaccine Cell Generation)

- Perform randomization prior to leukapheresis #1.
- CBC with differential and CD4+/CD8+ T cell ratio.
- Comprehensive metabolic panel
- For females of child-bearing potential, β -HCG serum pregnancy test.
- Infectious disease testing in accordance with institutional practices.
- Blood for immune monitoring.
- Dialysis type central venous catheter for patients with poor venous access.
- Oral Tums, 2 tablets, BID for 2 days prior to the leukapheresis procedure (if standard-of-care) to prevent the development of hypocalcemia from the citrate.
- Document adverse events.
- Document concomitant medications.

10.3 Chemoradiation

- For females of child-bearing potential, β -HCG serum pregnancy test within 72 hours prior to starting TMZ.
- Administer TMZ continuously from day 1 of RT to the last day of RT for a maximum of 49 days.
- Standard RT at the discretion of the treating Radiation Oncologist
- Radiation Therapy summary to include start and end dates, number of fractions, any interruptions, and total dose delivered.

10.4 Adjuvant TMZ Cycles

- History, physical & neurological exam
- Confirm eligibility prior to TMZ cycle 1.
- Administer Td booster with vaccine 1.
- Administer TMZ.
- Administer study vaccines.
- Perform vaccine site pretreatment with Td (1Lf) or saline intradermal prior to Vaccine #3, #6, and #9.
- Inguinal MRI/MRS imaging with Vaccine 3 (University of Florida site only). For women of childbearing potential a urine pregnancy test will be obtained prior to imaging.
- Blood for immune monitoring:
 - Leukapheresis 1
 - Prior to vaccine 1
 - Prior to vaccine 2
 - Prior to vaccine 3
 - At MRI/MRS imaging time points (UF site only)
 - Leukapheresis 2
 - Prior to vaccine 4
 - Prior to vaccine 7
 - Prior to vaccine 10

- At progression
- Urine for immune monitoring
 - Prior to vaccine 1
 - At MRI/MRS imaging time points (UF site only)

Patients seen by the neuro-oncology team between these vaccine visits may have blood drawn for immune monitoring at the discretion of the study team.

For immune monitoring, up to 80 mLs of blood will be collected in 10 yellow top tubes and processed in accordance with **SOP-UFBTIP-126**. For humoral response, approximately 3.5 mLs will be collected in a gold top tube.

- CBC with differential and CD4+/CD8+ T cell ratio at each vaccine visit and, if clinically indicated, at routine clinic visits.
- MRI (or CT) at the following time points:
 - bimonthly during TMZ cycles and every 3 months after the 12th TMZ cycle (or 1 year post surgery if TMZ discontinued prior to 12 cycles)
 - Response and progression will be assessed following Modified RANO Criteria as described in Section 11. Response Evaluation. Initial assessment of disease status will be done by the treating neuro-oncologist/study investigators, upon review of surveillance brain MRI during routine clinic visit followed by study vaccine administration or chemo cycle initiation. Clinical assessment of disease status will be followed by formal measurements of enhancing lesions for modified RANO criteria.
- Review and document adverse events at each visit.
- Review and document concomitant medications at each visit.

10.5 At Progression

- MRI (or CT) documenting progression.
- Blood for immunologic monitoring if feasible.
- Pathology slides (if available) consisting of 1 hematoxylin and eosin (H&E) and 19 unstained slides, prepared on Fischer Plus glass or Histostix coated slides.

10.6 Concomitant Medication

The following medications will be recorded with start date, stop date, and indication:

- Steroids
- Anticonvulsants
- Bevacizumab
- Any medication used in the treatment of a study drug related AE/SAE
- Any medication deemed to possibly be interactive with study drug by PI or designee.

Concomitant medication will be recorded at the time of vaccine #1 and continue until 30 days after the last dose of study drug and at leukapheresis time point.

Use of bevacizumab:

Bevacizumab is not a study drug on this trial. However, for patients who develop radiation necrosis symptoms, a short trial of bevacizumab can be considered at the discretion of the PI in consultation with the treating physician, if the PI believes that the patient may benefit from the treatment. Dose and frequency of bevacizumab treatment will be at the discretion of the investigator in keeping with standard of practice (bevacizumab 5-10 mg/kg every 2-3 weeks) for up to 3 months treatment.

NOTE: Bevacizumab is to be used for participants who develop symptomatic radiation necrosis, and is not intended to be used to treat the underlying tumor.

10.7 Schedule of Study Assessments

Footnotes on next page

Footnotes for Schedule of Study Assessments:

- 1 A diagnostic contrast-enhanced MRI or CT scan of the brain must be performed preoperatively and postoperatively. If no post op MRI/CT within 28 days of enrollment is available, a new brain MRI (or CT) must be obtained in order to determine residual burden and eligibility prior to randomization.
- 2 Negative serum pregnancy test within 72 hours prior to starting TMZ and negative urine pregnancy test prior to Inguinal MRI/MRS (UF site only).
- 3 1 H&E and 19 unstained slides from original surgery and at progression, if applicable.
- 4 Pre-leukapheresis testing in accordance with institutional practices.
- 5 Oral Tums, 2 tablets, for 2 days prior to leukapheresis (if standard-of-care).
- 6 Administer TMZ continuously from day 1 of RT to the last day of RT at a daily oral dose of 75 mg/m² for a maximum of 49 days.
- 7 Standard RT at the discretion of the treating Radiation Oncologist
- 8 Bimonthly during TMZ cycles and every 2 to 3 months after the 12th TMZ cycle (or 1 year post surgery if TMZ discontinued prior to 12 cycles). Measurements for all imaging will be recorded. Prior to vaccination, assessment for tumor progression can be made by the treating investigator, but all CT/MRI measurements for study endpoints must be made by designated study personnel.
- 9 CBC with differential and CD4+/CD8+ T cell ratio at each vaccine visit and, if clinically indicated, at routine clinic visits.
- 10 Up to 12 cycles of dose-intensified TMZ may be given. Cycle #1 should be started 4 (+/- 1) weeks after completing chemoradiation. Administer once per day for 21 consecutive days (days 1-21) of a 35 (+/- 7) day cycle. The starting dose for the first cycle will be 75 mg/m²/day, with a single dose escalation to 100 mg/m²/day in subsequent cycles if no adverse events are noted.
- 11 Within 14 days prior to initiation of TMZ and prior to subsequent TMZ cycles.
- 12 Randomization will occur prior to leukapheresis.
- 13 Administer vaccine #1 intradermally at day 22-24 after the first TMZ cycle. Vaccines #2 and #3 will occur at 2 (+/- 1) week intervals. Vaccines #4-10 will be given on day 22-24 of each TMZ cycle. Continue until a total of 10 vaccines have been administered or until tumor progression (whichever comes first). Each vaccination will be equally divided between both inguinal regions. Monitor for 30-60 minutes post-immunization for any adverse effects.
- 14 Up to 10 yellow top tubes (ACD-A) and 1 gold top tube (SST) during initial leukapheresis, prior to vaccines 1-3, during second leukapheresis, prior to vaccine 4, 7, 10, at MRI/MRS imaging time points (UF site only) and at progression if feasible. Peripheral blood will be processed in accordance with **SOP-UFBTIP-126**.
- 15 All patients will receive IM Td booster (5 Lf) with vaccine #1.
- 16 2 to 4 weeks after vaccine #3, repeat leukapheresis for DC or PBMC generation.
- 17 All patients will undergo vaccine site pretreatment with Td (1 Lf) or saline 6-24 hours prior to Vaccine #3, #6, and #9.
- 18 Patients at University of Florida site will undergo MRI/MRS imaging of inguinal draining lymph nodes before vaccine #3 site pretreatment, 48hrs post vaccination, and 5 to 7 days post vaccination (optional). Urine samples will be collected prior to vaccine #1 and at MRI/MRS imaging time points.
- 19 Within 7 weeks of surgery.
- 20 AE collection will begin at the time of administration of vaccine #1 and continue until 30 days after the last dose of study drug. Any adverse events associated with leukapheresis will also be recorded.
- 21 Including MMSE for patients age \geq 50 years.
- 22 Results from infectious disease markers performed within 30 days of enrollment can be used to satisfy criteria.
- 23 Additional leukapheresis may be performed if needed to generate additional vaccines.

11 RESPONSE EVALUATION

The modified RANO provides clinical guidelines for continuing therapy **beyond** suspected radiographic progression if the treating physician believes there may be a therapeutic benefit and provides criteria for defining progression and early drug failure while also allowing for the possibility of pseudoprogression (PsP) and pseudoresponse (PsR). An update to the RANO criteria proposes strategies to establish a general framework for response assessment in neuro-oncology that is agnostic to the mechanism of action of the particular therapy (anti-angiogenic, immunotherapy...) to address the challenges associated with interpretation of radiographic changes in patients with glioblastoma in clinical trials. The modified RANO proposes to **use the post-radiation time point as the baseline** for response evaluation and to consider only objectively defined, measurable enhancing disease in the definition of response and progression (i.e. exclusion of qualitative assessed T2/FLAIR changes)

11.1 General Methodology for Determining Tumor Measurements

[figure not shown]
Newly diagnosed GBM patients will initially undergo a pre-entry MRI scan for initial diagnosis prior to entry in the study and prior to therapy. The post-operative scan will determine residual enhancing disease which may be used as a covariate in survival analyses. Patients will then start on standard therapy, Temozolomide with concurrent radiation therapy (RT). **The Post-RT scan will be required and used as the baseline scan** for which response will be determined. Following the first cycles of adjuvant therapy, patients will receive additional required MRI scans.

All radiographic responses will be based on MRI scans of the brain obtained with and without contrast. Tumor size will be based on the product of the maximal diameters in 2 different planes. Response will be assessed as a percentage change in tumor size from baseline. Tumor measurements in the follow-up scans will be compared to those of the post-RT scan to document response.

Definition of Measurable Disease, Non-Measurable Disease, and Target Lesions

Measurable disease should be defined as contrast enhancing lesions with a minimum size of **both** perpendicular measurements greater than or equal to 10mm (if the largest diameter is greater than 10mm but the perpendicular diameter is less than 10mm, this would constitute non-measurable disease). Up to a total of five target measurable lesions should be defined and ranked from largest to smallest.

Algorithm for identifying measurable and target lesions:

11.2 Complete Response (CR)

Requires **all** of the following:

1. Disappearance of all enhancing measurable and non-measurable disease sustained for at least 4 weeks. The first scan exhibiting disappearance of all enhancing measurable and non-measurable disease is considered “preliminary CR”. If the second scan exhibits measurable enhancing disease with respect to the “preliminary CR” scan, then the response is not sustained, noted as pseudoresponse, PsR, and is now considered “preliminary PD” (note: confirmed PD requires at least two sequential increases in tumor volume). If the second scan continues to exhibit disappearance of enhancing disease or emergence of non-measurable disease (less than 10mm bidimensional product), it is considered a *durable CR* and the patient should continue on therapy until confirmed PD is observed.
2. Patients must be off corticosteroids (or on physiologic replacement doses only).
3. Stable or improved clinical assessments.

Note: Patients with non-measurable disease only at baseline cannot have CR; the best response possible is stable disease (SD).

11.3 Partial Response (PR)

Requires *all* of the following:

1. $\geq 50\%$ decrease in sum of products of perpendicular diameters of all measurable enhancing lesions compared with baseline, sustained for at least 4 weeks. The first scan exhibiting $\geq 50\%$ decrease in sum of products of perpendicular diameters of all measurable enhancing lesions compared with baseline is considered “preliminary PR”. If the second scan exhibits PD with respect to the “preliminary PR” scan, then the response is not sustained, noted as pseudoresponse, PsR, and is now considered “preliminary PD” (note confirmed PD requires at least two sequential increases in tumor volume). If the second scan exhibits SD, PR, or CR, it is considered a *durable PR* and the patient should continue on therapy until confirmed PD is observed.
2. Steroid dose should be the same or lower compared with baseline scan.
3. Stable or improved clinical assessments.

Note: Patients with non-measurable disease only at baseline cannot have PR; the best response possible is stable disease (SD).

11.4 Stable Disease (SD)

Requires *all* of the following:

1. Does not qualify for complete response, partial response, or progressive disease. Note this also applies to patients that demonstrate PsR when the confirmation scan does not show PD or PsP when the confirmation scan does not show PR/CR.

In the event that corticosteroid dose was increased (for new symptoms/signs) without confirmation of disease progression on neuroimaging, and subsequent follow-up imaging shows that the steroid increase was required because of disease progression, the last scan considered to show stable disease will be the scan obtained when the corticosteroid dose was equivalent to the baseline dose.

11.5 Progressive Disease

Defined by *any* of the following:

1. At least two sequential scans separated by at ≥ 4 weeks both exhibiting $\geq 25\%$ increase in sum of products of perpendicular diameters of enhancing lesions. The first scan exhibiting $\geq 25\%$ increase in sum of products of perpendicular diameters of enhancing lesions should be compared to the smallest tumor measurement obtained either at baseline (if no decrease) or best response (on stable or increasing steroid dose) and is noted as “preliminary PD.” If the second scan at least 4 weeks later exhibits a subsequent $\geq 25\%$ increase in sum of products of perpendicular diameters of enhancing lesions relative to the “preliminary PD” scan, it is considered “confirmed PD” and the patient should discontinue therapy. If the second scan at least 4 weeks later exhibits SD or PR/CR, this scan showing “preliminary PD” is noted as “pseudoprogression”, PsP, and the patient should continue on therapy until a second increase in tumor size relative to the PsP scan is observed. Note that any new *measurable* ($>10\text{mm} \times 10\text{mm}$) enhancing lesions should *not* be immediately considered PD, but instead should be added to the sum

of bidimensional products or total volume representing the entire enhancing tumor burden.

2. In the case where the baseline or best response demonstrates no measurable enhancing disease (visible or not visible), then any new *measurable* ($>10\text{mm} \times 10\text{mm}$) enhancing lesions are considered PD *after* confirmed by a subsequent scan ≥ 4 weeks exhibiting $\geq 25\%$ increase in sum of products of perpendicular diameters of enhancing lesions relative to the scan first illustrating new measurable disease. The first scan exhibiting new measurable disease is noted as “preliminary PD.” If the second scan at least 4 weeks later exhibits a subsequent $\geq 25\%$ increase in sum of products of perpendicular diameters of enhancing lesions relative to the “preliminary PD” scan it is considered “confirmed PD” and the patient should discontinue therapy. If the second scan at least 4 weeks later exhibits SD, CR, PR, or becomes non-measurable, this scan showing “preliminary PD” is noted as “pseudoprogression”, PsP, and the patient should continue on therapy until a second increase in tumor size relative to the “preliminary PD”, or PsP, scan is observed. Note that any new *measurable* ($>10\text{mm} \times 10\text{mm}$) enhancing lesions on the subsequent scan following the preliminary PD scan should *not* be immediately considered confirmed PD, but instead should be added to the sum of bidimensional products or total volume representing the entire enhancing tumor burden.
3. Clear clinical deterioration not attributable to other causes apart from tumor (e.g. seizures, medication adverse effects, therapy complications, stroke, infection) or attributable to changes in steroid dose.
4. Failure to return for evaluation as a result of death or deteriorating condition.

11.6 Symptomatic Deterioration & Reporting Clinical Status

Patients with global deterioration of health status requiring discontinuation of treatment without objective evidence of disease progression at that time, and not either related to study treatment or other medical conditions, should be reported as PD due to “symptomatic deterioration.” Every effort should be made to document the objective progression even after discontinuation of treatment due to symptomatic deterioration.

Neurological exam data should be provided to the study designated neuro-radiologists as “stable, improved, declined” in case report forms. Clinical status should be recorded as “declined” if the neurological exam is worse, otherwise the clinical status should be set to “improved” or “stable”. In the event that necessary clinical data is not available, clinical status should be recorded as “not available” and that particular time point can only be reviewed for PD (otherwise “non-evaluable”). Neurological data must be within ± 7 days of the time-point response date, otherwise the data is considered “not available”.

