11.8 Overall Objective Status

The overall objective status for an evaluation should be determined by combining the patient's radiographic response on target lesions, new disease, neurological status, and steroid dose/usage as defined in the table [below](#) for patients with *measurable* ($>10\text{mm} \times 10\text{mm}$) disease. Note that patients with possible PsP or pseudoresponse should be given the Objective Status of "Preliminary Progression" or "Preliminary Response", respectively. Once PsP, pseudoresponse, or true progression/response are confirmed, the Objective Status can be changed accordingly.

[figure not shown]
Guidelines for determining comprehensive objective status

Target lesions (current scan)	Target lesions (previous scan)	New sites of measurable disease ^a	Neurological status	Steroid usage	Steroid dose	Overall objective status
CR	Not Evaluated	No	Stable/Better	No	N/A	Preliminary CR
PR	Not Evaluated	No	Stable/Better	Any	Stable/Decreasing	Preliminary PR
PD	Not Evaluated	Yes or No	Stable/Better	Any	Stable/Increasing	Preliminary PD
PD	Preliminary or Confirmed PR/CR	No	Stable/Better	Any	Stable/Increasing	Preliminary PD
SD	Preliminary or Confirmed CR/PR or SD/NE	No	Stable/Better	Any	N/A	SD
PR	Preliminary PR	Yes or No	Stable/Better	Any	Stable/Decreasing	Confirmed PR
SD	Preliminary PR	Yes or No	Stable/Better	Any	Stable/Decreasing	SD (Preliminary PR → Confirmed PR)
SD	Preliminary CR	Yes or No	Stable/Better	Any	Stable/Decreasing	SD (Preliminary CR → Confirmed CR)
CR	Preliminary CR	No	Stable/Better	No	N/A	Confirmed CR
SD	Preliminary PD	No	Stable/Better	Any	Stable/Decreasing	SD (Confirmed PsP)
CR/PR/SD PD/NE	CR/PR/SD/PD/NE	Yes or No	Worse	Any	Stable/Increasing	Confirmed PD
PD	Preliminary PD	Yes or No	Any	Yes	Stable/Increasing	Confirmed PD

^aNote that new sites of measurable disease are added to the sum of bidimensional products or total lesion volume, or constitutes preliminary PD in the case of no measurable disease at baseline or best response

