13 SAFETY MONITORING AND REPORTING

13.1 Dose-limiting Toxicity

DLTs will be evaluated according to NCI CTCAE (Version 5.0) criteria.

A DLT will be defined as a possibly, probably or definitely drug-related:

- Grade IV toxicity (with the exception of grade IV cerebral edema) or any non-neurologic toxicity \geq Grade III toxicity of any duration.
- Grade III neurologic toxicity if not improved to Grade \leq II within 7 days of clinical management will be declared a DLT.

Neurotoxicity that improves to Grade II within 7 days will be allowed an additional 21-day management period to resolve to a Grade I or return to patient baseline. If the event does not improve to a Grade I or return to patient's baseline within 21 days of management, it will then be declared a DLT

Immune-related neuro toxicities are a recognized adverse event associated with immunotherapy. Symptoms may present throughout the course of treatment and involve the peripheral and central nervous system, and usually respond well to steroids, if started early. Early recognition of neurological toxicity is critical for the initiation of clinical management or surgical intervention to prevent or potentially reverse neurological sequelae. If neurological toxicity improved to \leq Grade I within 28 days of clinical management, patient may resume treatment.

Non-neurologic Grade III and any Grade IV toxicity or any life-threatening event not attributable to a concomitant medication, co-morbid event, or disease progression, even if reversible, will be considered a DLT. If biopsy cannot be obtained, any new radiographic or clinical changes not attributable to tumor progression that produce a non-neurologic Grade III or any Grade IV or life-threatening toxicity will be considered a DLT. Life-threatening events, as described above, even if considered a Grade III toxicity, will still be considered a DLT even if reversible and in such cases no further vaccinations will be given.

If a **neurologic Grade III NCI CTC toxicity** is seen that is not attributable to a concomitant medication, co-morbid event, or disease progression that has been documented radiographically or clinically, the next immunization for that patient will be withheld for up to 2 months or until the NCI CTC toxicity improves to a Grade \leq I or until the KPS score returns to within 10 points of

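### For patients with measurable disease, the 11.8 status table scores a worse neurological exam as confirmed progression whatever its cause, against 11.5 and the first paragraph of 11.6, and 15.3.1 does not say which rule sets the PFS event

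*Combined protocol and SAP*

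**What the plan says.** Four parts of the combined protocol and SAP bear on this.

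- **11.5, item 3** accepts clinical deterioration as progression only on a condition: "Clear clinical deterioration not attributable to other causes apart from tumor". Its examples of other causes are seizure, drug side effects, complications of therapy, stroke and infection. Deterioration due to a steroid change is also ruled out.
- **11.6** has two paragraphs. The first reserves progression by symptomatic deterioration for decline that is related neither to study treatment nor to another medical condition. The second sets the coding: "Clinical status should be recorded as “declined” if the neurological exam is worse". It also fixes what goes to the readers: "Neurological exam data should be provided to the study designated neuro-radiologists as" stable, improved or declined. The neurological data must fall within 7 days either side of the time-point.
- **11.8** says that overall status "should be determined by combining the patient's radiographic response on target lesions, new disease, neurological status, and steroid dose/usage", using a table for patients with measurable disease headed "Guidelines for determining comprehensive objective status". One row covers a current and a previous scan result of CR, PR, SD, PD or NE, with or without new disease, and ends: "Worse Any Stable/Increasing Confirmed PD".
- **15.3.1** runs PFS from first vaccination to the first documented progression or recurrence, or to death. It does not say whether 11.5 or the 11.8 table decides that progression has been documented.

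**The concern.** The definition asks why the patient is worse; the table does not. A patient in complete response whose exam is worse after a seizure has not progressed under 11.5 item 3, but has confirmed progression under 11.8. Nor can a reader working from the three-level status apply the 11.5 condition, because cause is not among the items that 11.6 sends.

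The protocol expects such patients. Section 13.1 describes immune-related neurotoxicity that usually responds to steroids and after which treatment may resume. Section 10.6 provides for symptomatic radiation necrosis and distinguishes it from treatment of the tumour. Either patient, if worse on examination close to a scan and with steroids unchanged or raised, fits the row.

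At stake is the PFS comparison, a secondary objective. False events in all arms pull the hazard ratio towards 1. False events concentrated in Arms 1 and 2 push it against the vaccine.

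**Working it through.** **Text check.** Take every input the table uses when the exam is worse and steroids are not decreasing: 5 current results × 5 previous results × new disease yes/no × steroid use yes/no × dose stable/increasing = 5 × 5 × 2 × 2 × 2 = 200 combinations. All 200 fall in the row that gives confirmed progression. The only other row that admits a worse exam (progression after preliminary progression, any neurological status) has the same outcome. No row covers a worse exam with a decreasing steroid dose. The table has no cause column and no footnote to 11.5.

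**Does another section settle it?** Section 11.10 allows clinical judgement, but only for radiographic change in clinically stable or improved patients, so it excludes this case. Section 11.11 depends on tissue and does not amend the row. Section 15.3.1 gives no order of precedence.

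**Size.** The plan states no sample size or power for PFS, so there is no figure to reproduce. The 77-death calculation in 15.2 concerns overall survival and is not touched. The illustration below rests on assumptions that are not in the documents: exponential PFS, control median 8 months, 24 months of follow-up, and a fraction p of patients assigned a non-tumour decline scored as progression at a time uniform over 0 to 7 months.

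- Control hazard = ln 2 / 8 = 0.0866 per month. Vaccine hazard at a true ratio of 0.60 = 0.60 × 0.0866 = 0.0520.
- Patients without a false event: events per patient E0 = 1 − exp(−24λ), person-time P0 = E0/λ. Vaccine: 0.7128 and 13.712 months. Control: 0.8750 and 10.099 months.
- Patients assigned a false event: one event each, mean time P1 = 1/λ − (1 − exp(−7λ))/(7λ²). Vaccine: 3.111 months. Control: 2.888 months.
- Observed rate = [(1 − p)E0 + p] / [(1 − p)P0 + pP1].

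Vaccine group, p = 0.05: 0.7272 / 13.182 = 0.0552. Divided by 0.0866, this gives 0.64. Control group, p = 0.05: 0.8812 / 9.738 = 0.0905. If both groups are affected, 0.0552 / 0.0905 = 0.61.

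| p | True 0.60, vaccine arms only | True 0.60, all arms equally | True 1.00, vaccine arms only | True 1.00, all arms equally |
|---|---|---|---|---|
| 2.5% | 0.62 | 0.60 | 1.02 | 1.00 |
| 5% | 0.64 | 0.61 | 1.04 | 1.00 |
| 10% | 0.68 | 0.62 | 1.09 | 1.00 |

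Of the planned 80 vaccine patients, 2.5%, 5% and 10% are 2, 4 and 8.

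**The case against.** The strongest reply is that the protocol does exclude non-tumour decline, twice: in 11.5, the section that defines progression, and in the first paragraph of 11.6. The 11.8 table is headed as guidelines, so a careful reader would let the definition prevail. That is a reasonable reading, but nothing in the text requires it: 11.8 says status should be determined from the table, and the readers are not given the cause.

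Second, the synopsis and 9.1 call for histological documentation of progression unless contraindicated, so that inflammatory clinical changes are not mistaken for it. This is a real safeguard where tissue is obtained, and it would be wrong to say that the plan has no check. It does not cover every patient and changes neither the row nor the PFS definition.

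Third, the reach is limited, and this stands. The table covers measurable disease only, and the trial includes patients without it after gross total resection. A seizure or infection does not trigger the row by itself: the exam must be worse within 7 days of the time-point, and scans are bimonthly in the first year.

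Fourth, 5 to 10% in the vaccine arms alone has no source. The 20201201 entry in the summary of changes reports 2 immunotherapy-associated events of Grade 3 or greater among all treated subjects, of unstated type. Two of the planned 80 is 2.5%. That count does not bound the problem, since the row needs only a worse exam of any grade or cause, but it does make the upper figures less likely for treatment-related decline.

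**Conclusion.** The contradiction is in the current text and holds for patients with measurable disease. If the row is applied as written, some declines that 11.5 item 3 excludes become PFS events. How many is unknown. Under the assumptions above, a true hazard ratio of 0.60 is observed as 0.62 to 0.68 if false events fall in the vaccine arms only, at 2.5 to 10%. At 5 to 10% in all arms alike it is 0.61 to 0.62, and a true 1.00 then stays at 1.00.

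A reader might infer three stronger things that the documents do not support:

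- **That every toxicity, seizure or infection becomes a PFS event.** This would need the table to override 11.5 and 11.6 in all patients. No text says so, and the scope and timing limits narrow it further.
- **That a progression code removes an event from toxicity assessment.** Section 13.1 does set aside neurologic Grade III toxicity attributable to progression documented clinically. But dose-limiting toxicity rests on drug-relatedness, 13.3 has the PI assign attribution and requires all events of Grade 3 or greater to be recorded whatever the cause, and nothing lets a table code replace that judgement.
- **That the primary result is affected.** Overall survival does not use these criteria.

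**What to change.** Reconcile 11.5 item 3, 11.6 and 11.8, and state in 15.3.1 which of them defines the PFS event. For PFS scoring:

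1. Send one further item with the clinical status: decline attributable to tumour, to another cause listed in 11.5 item 3, or undetermined.
2. Make the 11.8 row for a worse exam subject to 11.5 item 3, and state in advance how undetermined cases are scored.
3. List the affected cases and report PFS with and without them.

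The cost is one case report form item, one qualifier on a table row and one sentence in 15.3.1. Sites already assign causality to adverse events under 13.3. The downside is that attribution is a clinician's judgement in a single-blind trial and may itself be influenced by the arm; the listing and the paired PFS analyses are there to expose that.

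Confirmed progression also stops therapy under 11.5 and 11.9. The sponsor must reconcile that consequence with the same passages. The change proposed here is confined to endpoint scoring and proposes no clinical rule.
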